4.7.3 Data Collection and Follow-up for Withdrawn Subjects

Withdrawn patients after enrollment will be analyzed as intention to treat. Missing data will be imputed using multiple imputations along with sensitivity analyses for missingness according to the recommendations given in the National Research Council report.¹²⁹

5 Study Procedures

5.1 Prior and Concomitant Therapy

All concomitant antihypertensive medications prescribed by the patient's healthcare team are permitted during the study. Ongoing antihypertensive medication changes by the patient's healthcare team (including medication initiation, discontinuation, and/or dose changes) are allowed throughout the study.

All other medications, supplements, and lifestyle modifications that were part of the participant's treatment plan prior to the study are included.

The participant may also be started on non-pharmacologic therapy (examples: physical activity, stress management) by their medical team during this study.

5.2 Randomization and Blinding of Intervention

Randomization assignments for both sites will be generated by the UW Biostatistics Clinical Trials Statistical Data Analysis Center stratified by research site, in block sizes of 4 and 6 to ensure equal allocation. The Research Electronic Data Capture (REDCap) clinical data management system will be used to verify eligibility and data completeness prior to randomization. The UW Biostatistics team will develop a randomization list, which will be provided to the MyHEART research staff in a binder. There will be two people responsible for the binder at all times at HIP (PI and research manager) who will give the randomization assignment upon receiving a phone call from the

research assessor (from either site) conducting Visit 2. Until the staff receives a phone call, the binder will remain in a locked file cabinet, separate from other research materials, within a locked office at [name] (HIP).

All study participants will have contact with research staff (e.g., research coordinators, research visit study assessment staff). To reduce bias, MyHEART 6- and 12-month assessors will be blinded to treatment assignments.¹³⁰ Assessors will be trained to treat patients in both study groups identically per protocol.¹³¹ Ambulatory monitoring will be the gold standard for blood pressure measurements.

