1. History of medically determined Congestive Heart Failure
2. Unable to provide informed consent (i.e. , activated healthcare power of attorney)
3. Unable or unwilling to travel to local clinic for research visits
4. Currently residing in a skilled nursing facility
5. Diagnosed with sickle cell anemia or cystic fibrosis
6. Diagnosed with stroke, myocardial infarction, and/or coronary artery revascularization in the past 2 years
7. Syncope while exercising or doing strenuous activity within past 12 months
8. Currently prescribed warfarin, novel oral anticoagulant, or insulin
9. Planned organ transplant or prior transplant in the past 5 years
10. Chemotherapy or radiation therapy within 6 the past months
11. Severely impaired hearing, vision, or speech, as determined by study staff responsible for enrollment
12. Current participation or planning to participate in another clinical trial in the next 12 months
13. Pregnant or planning to become pregnant in the next 12 months
14. Planning to leave the geographic area in the next 6 months
15. Health condition that will limit both increasing physical activity and changing diet
16. Illegal drug use (other than marijuana) in the past 30 days

17. Unable to read or communicate in English
18. Currently on dialysis or seeing a Nephrologist
19. Unaware or denies history of high blood pressure or hypertension
20. Between-arm blood pressure difference ≥ 20 mmHg
21. White Coat Hypertension (24-hour ambulatory monitoring)
22. Inability to comply with or complete the protocol or other reasons at the discretion of the principal and site investigators
23. Prisoners

This list of medical conditions or conflicting medications was selected to exclude patients who might experience harm from participation. Patients with advanced chronic kidney disease (on dialysis or seeing a nephrologist) or congestive heart failure are excluded due to stringent dietary restrictions. Illegal drug use (except marijuana) in the past 30 days will result in ineligibility; illegal drug use will not be recorded.

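### Section 5.2 describes nothing that hides upcoming assignments from the two binder custodians, one of them the PI, and the Visit 2 text lists randomisation before the self-report baselines used in Aim 2

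*Combined protocol and SAP*

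**What the plan says.** **Custody of the list (section 5.2).** The statistics group generates the assignments, stratified by site and "in block sizes of 4 and 6 to ensure equal allocation". Then: "The UW Biostatistics team will develop a randomization list, which will be provided to the MyHEART research staff in a binder". The PI and the research manager are jointly responsible for it, and it is they "who will give the randomization assignment upon receiving a phone call" from the assessor conducting Visit 2 at either site. On storage: "Until the staff receives a phone call, the binder will remain in a locked file cabinet", inside a locked office. REDCap is to "verify eligibility and data completeness prior to randomization".

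**Discretion over eligibility.** Exclusion criterion 22 in section 4.3 allows exclusion for "other reasons at the discretion of the principal and site investigators". Under section 4.4.1 the PI helps to define the candidate list from the health record, but research coordinators lead eligibility assessment, consent and enrolment.

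**Order at Visit 2.** Section 5.4.1.1 names enrolment, then randomisation, then completion of the baseline assessment. The Visit 2 row of the table in 5.4.3 puts clinic blood pressure and monitor removal first, then enrolment and randomisation, then the baseline questions and assessment.

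**Blinding.** Section 5.2 says that "MyHEART 6- and 12-month assessors will be blinded to treatment assignments". Section 2.5.6 says more broadly that staff who interact with enrolled participants will be blinded.

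**Measures and analysis.** Section 5.4.1.2 places the Godin questionnaire and ASA24 under interviewer-administered collection at baseline, 6 and 12 months, although ASA24 is described as self-administered and automatically coded. Section 6.2 analyses the Aim 2 outcomes as differences from baseline to 6 months.

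**The concern.** There are two separate issues, both at the moment of randomisation.

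**(a) Custody.** Concealment works when nobody who can influence whether a patient enters the trial can know the next assignment. The safeguards in 5.2 achieve this for the site assessors. They are not described as achieving it for the custodians, and one custodian also holds a discretionary power to exclude.

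**(b) Order.** A baseline value is safe to subtract or adjust for when it is fixed before the arm is known. If a self-reported baseline is taken after the randomisation call, the interviewer knows the arm and the participant may know it too. Any difference in reporting then enters the baseline, and from there the Aim 2 comparisons and the exploratory Aim 3, in either direction. The recall periods largely precede randomisation, so the worry is how behaviour is reported, not a change in the behaviour itself.

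**Working it through.** The point rests on procedure and on no sample size or power figure in the plan. The passages are set side by side first; two short calculations follow.

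**1. Who can see the next entry?**
- Site assessors cannot: they phone in, and the binder is locked away.
- For the two custodians, 5.2 describes physical storage and release on a call. It describes no sealed or covered entries and no system-held allocation.
- The PI is both a custodian (5.2) and a holder of discretion (criterion 22). The site investigators share that discretion but are not named as custodians.

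**2. How predictable is the next entry?**
Inputs: blocks of 4 and 6 with equal allocation (5.2). Assumption: the two sizes are used equally often. For a block of size 2m, a person who knows all earlier assignments at the site and guesses optimally is right for this share of entries:

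(m + 2^(2m−1)/C(2m,m) − 0.5)/(2m)

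- Block of 4 (m = 2): (2 + 8/6 − 0.5)/4 = 2.833/4 = 70.8%
- Block of 6 (m = 3): (3 + 32/20 − 0.5)/6 = 4.1/6 = 68.3%
- Both sizes: (2.833 + 4.1)/10 = 69.3%

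A simulation in which the guesser does not know which block size is in progress also gives about 69%. A readable list gives 100%, and chance gives 50%. Masking the entries would therefore take a custodian who tracks past assignments from 100% to about 69%, not to 50%.

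**3. What order does the text give at Visit 2?**
- Sections 5.4.1.1 and 5.4.3 agree: randomisation, then baseline assessment.
- Section 3.1.1 fits this timing. It contrasts baseline with follow-up, where questionnaires are done at the first visit of each pair.
- The completeness check in 5.2 does not say which data it covers. If it covers the baseline assessment, it conflicts with 5.4.1.1 and 5.4.3. If it does not, their order stands. Either way the sections need reconciling.

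**4. Which baselines are exposed?**
- Clinic and ambulatory pressure: listed before randomisation, so not exposed.
- Godin: interviewer-administered, so the most exposed.
- ASA24: self-administered and automatically coded, so exposed only through the participant's own knowledge of the arm.
- Competence, autonomy and motivation scales: exposed only if collected at that point.
- Weight and BMI: measured, so less exposed.

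**5. How would a reporting shift carry through?**
Take a measure with unit variance, a baseline reporting shift of s SD in one arm only, and a baseline to follow-up correlation r. The absolute bias is s for the change score and r·s for ANCOVA. The documents give neither s nor r.

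The benchmark is the Aim 2 planning effect in 6.1, 0.4 SD of the differences. Its stated 90% power reproduces: 132 per arm at two-sided 0.05 gives 0.90. On the scale of the measure, the effect is 0.4·√(2(1−r)), which is 0.473 SD at r = 0.3 and 0.310 SD at r = 0.7.

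| Assumed s | ANCOVA bias as share of planning effect (r = 0.3 to 0.7) | Change-score bias as share of planning effect (r = 0.3 to 0.7) |
|---|---|---|
| 0 | 0% | 0% |
| 0.1 | 0.03/0.473 = 6% to 0.07/0.310 = 23% | 0.1/0.473 = 21% to 0.1/0.310 = 32% |
| 0.2 | 0.06/0.473 = 13% to 0.14/0.310 = 45% | 0.2/0.473 = 42% to 0.2/0.310 = 65% |

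Every s and r here is assumed. The table shows how a shift would pass through, not that one exists.

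**The case against.** **On custody.** A reader might infer that assignments are definitely open to the PI, or that the PI could steer enrolment. The documents do not support either. The format of the binder entries is not described, so the lack of masking is inferred from silence. Coordinators lead eligibility assessment. Under 5.4.1.1 the ambulatory result that decides eligibility at Visit 2 is read by someone other than the person consenting or enrolling. Eligibility is also checked in REDCap before randomisation. No section has the PI judging individual patients at Visit 2, so the route is a general discretion clause. This stands, and it makes the route narrow. It does not close it, because 5.2 is where concealment is specified and it stops at locks and a phone call.

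**On order.** A reader might infer that the baselines are certainly taken after randomisation. They are given in list order, not as an instruction. The visit table is loosely drafted: its 12-month row refers to a 6-month assessment, and its 21-day limit for Visit 2 differs from the 30 days in 5.4.1.1. If its baseline screening questions concern eligibility, they cannot literally follow randomisation. The completeness check in 5.2 can fairly be read as covering baseline data. The study calendar, procedures flowchart and full SAP are appendix items that were not available for review and may settle the order. All this stands as a reason for caution. It does not remove the need to reconcile 5.2 with two sections that agree with each other.

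**On the participant's knowledge.** Section 5.4.5 has participants told their assignment at 12 months. Against that, 5.4.1.2 has intervention participants trained on the home monitor at the baseline visit, which would reveal the arm, but no section places that training before the questionnaires. Participant knowledge at that moment is therefore possible but not established. The assessor's knowledge follows directly from the phone call.

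**Conclusion.** The point holds as a cheap improvement to make, with medium confidence.

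(a) The custody described leaves the PI, who shares discretion to exclude, and the research manager able to know upcoming assignments unless the entries are masked in a way that 5.2 does not mention. How often discretion would be used is unknown, and no effect on results is shown.

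(b) If Visit 2 runs as listed, the Aim 2 self-report baselines, chiefly Godin and possibly ASA24, are collected after the assessor learns the arm. Any bias in the change-from-baseline comparisons cannot be sized from the documents and may be zero. The percentages in the working rest wholly on assumed inputs and should not be cited as an estimate.

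It would be wrong to extend (b) to the co-primary outcomes: their baseline pressures are listed before randomisation. The mismatch between 2.5.6 and 5.2 on who is blinded is visible in the text and needs no inference.

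**What to change.** - **Sections 5.4.1.1 and 5.4.3:** state that eligibility is confirmed and all baseline questionnaires and measurements are completed before the randomisation call, with arm-specific monitor training afterwards.
- **Section 5.2, completeness check:** state that the REDCap check covers those baseline data.
- **Section 5.2, custody:** hold the list at the Biostatistics centre or in REDCap, away from anyone with discretion over eligibility. Masking the binder entries is a partial alternative: the custodians release assignments for both sites and could track them, which leaves the 69% figure above.
- **Section 2.5.6:** align it with 5.2, naming who learns the assignment and who stays blinded.
- **If the appendix calendar already sets this order:** cite it in 5.2 and correct 5.4.1.1 and the visit table to match.

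The cost is minor set-up work for list custody (least if the entries are only masked, for less protection) and a later call within Visit 2. Visit content and the number of visits do not change.

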5.3 Established Standard of Care

Usual care and intervention arm participants will receive routine hypertension clinical care per their primary care provider. This includes the possibility of receiving untailored self-management resources (i.e., dietitian referral) at their provider's discretion, but this is not systematically tailored to young adults' needs. These patients would be treated according to current hypertension guideline standards including, but not limited to, hypertension lifestyle modification counseling: 1) reduced sodium intake, 2) weight loss, 3) reduced alcohol consumption, and 4) increased physical activity. This may include verbal discussions and/or handouts. Medications would be initiated and/or titrated per hypertension guidelines.

All patients would have clinic blood pressure checks and would be encouraged to have home blood pressure monitoring. Additionally, providers may order 24-hour Ambulatory Blood Pressure Monitoring, per the U.S. Preventive Services Task Force guidelines, to exclude white coat hypertension. Patients would also have additional tests not limited to blood draws, EKGs, echocardiograms, etc.

We will assess the number of healthcare team contacts in the usual care arm by calculating the number of primary care and specialty visits and dietitian and exercise referrals after study enrollment (see IRB application with data variable sheet).^{50,60} Usual care arm participants will receive AHA's "What is High Blood Pressure"¹³¹ handout (copies of handouts are in the Appendix).¹³² It is usual care for patients to receive hypertension educational material when presenting for a hypertension visit. They will not receive home blood pressure monitors. Usual care participants will have the same 6- and 12-month assessments as the intervention arm.

5.4 Study Visits

Study Calendar - see appendix

5.4.1 Screening/Baseline:

The same procedures will be followed at both research sites (Madison and Milwaukee).

5.4.1.1 Screening Visits:

Screening Visit 1: Screening Visit 1 occurs no more than 1 month after the telephone screening phone call. Written informed consent and HIPAA authorization will be obtained at the start of Screening Visit 1, which will include authorization for additional screening/eligibility assessment¹³³ (e.g., 24-hour ambulatory blood pressure monitoring), gathering data, including information from the electronic health record, and all study procedures after enrollment, if eligible. If a potentially eligible patient requests to reschedule to sign the consent and/or HIPAA form, they may do so within 30 days of the screening phone call. Blood pressures will be measured. The patient is not eligible if the between-arm blood pressure difference is ≥ 20 mmHg. If these findings are noted, the participant will receive an incidental finding notification to discuss with their primary care provider. All patients

[figure not shown]

Figure 1. 24-Hour Ambulatory BP Monitoring

will be given their clinic blood pressure in written format from Visit 1, regardless of eligibility. Remaining eligible patients will receive an ambulatory blood pressure (AMBp) monitor (example: SpaceLabs; final product to be determined in the appendix)¹³⁴ for 24-hour blood pressure monitoring. The selected AMBp device will be FDA approved or have a 510(k) clearance. 24-hour AMBp monitoring is recommended to confirm a hypertension diagnosis (exclude white coat hypertension).¹³⁵⁻¹³⁸ The U.S. Preventive Services Task Force noted up to 65% of patients with high office blood pressures were not diagnosed with hypertension after AMBp monitoring.¹³⁹ Previous young adult focus groups supported AMBp monitoring (see Figure 1) given its mobility and limited time commitment.

If a potentially eligible young adult already completed 24-hour ambulatory blood pressure monitoring through their UW Health or Aurora Health Care Clinic within the past 3 months, they do not need to repeat 24-hour ambulatory blood pressure monitoring for study eligibility. The ambulatory blood pressure monitoring report will be reviewed in their electronic health record to evaluate for white coat hypertension (an exclusion criteria). If eligible, the participant will be able to proceed with the Screening Visit 2/Baseline Assessment Visit. The individual's honorarium for Visit 1 and Visit 2 will not be adjusted/decreased.

Screening Visit 2/Baseline Assessment Visit: After receiving a 24-hour AMBp monitor, participants will be asked to return for Visit 2 on the next business day. Participants will have up to 30 days from Screening Visit 1 to return for Visit 2 without having to restart with the telephone screening process. A research staff member (not the individual acquiring consent or enrolling during this visit) will evaluate the mean 24-hour ambulatory blood pressure. If there is white coat hypertension, the patient is ineligible, and will receive an incidental finding letter to share with their primary care provider. Remaining eligible patients will be enrolled, randomized to MyHEART or usual care, and complete the baseline assessment.

5.4.1.2 Baseline/Follow-Up Data Collection:

All research staff will be trained in all key elements of the protocol and use of the data management system.

Anthropometric Measurements

- **Height** will be determined at each assessment visit using a wall-mounted stadiometer, without shoes or other outdoor footwear. Two measures of height will be taken and the average of the two will be used. We will repeat the measurement of height at each assessment visit because growth may still be occurring in young adults. Height will be measured to the nearest 0.1 cm.
- **Weight** will be determined at each assessment in light indoor clothes, removing all excess layers of clothing, and without shoes at all visits. All scales will be calibrated using standard weights, annually by the Bureau of Weights and Standards and quarterly by trained study personnel. Weight will be measured to the nearest 0.1 kg.
- **Body mass index (BMI)**. The weight and height measures will be used to calculate Body Mass Index (weight in kilograms divided by height in meters squared; kg/m²)
- **Waist Circumference** will be measured at baseline per established protocol/figures in the appendix.

Baseline Self-Reported Measures

All of the following measures will be recorded on paper by the participant, then electronically entered, with confirmation of correct entry, by the research staff via REDCap on an encrypted research computer within the research offices at UWHC and/or HIP. **See appendix for final forms and questions.**

- **Alcohol Use:** Alcohol consumption will be evaluated by alcohol beverage type and quantity as performed in the CARDIA (Coronary Artery Risk Development in Young Adults) cohort study; answered by self-report.¹⁴⁰
- **Financial Status:** Participants will self-report their financial situation by selecting, for example, whether they: a) had enough money after paying bills for extra things (e.g., dining out), b) enough to pay bills but not to purchase extra things, c) enough money to pay bills by cutting back on things, or d) difficulty paying bills no matter what was done. The first two answer choices are categorized as "adequate income" and the last two choices as "inadequate income".³² This financial assessment accounts for varying income, which is more reflective of young adulthood.

- **Annual Household Income:**¹⁴¹ income will be divided into six categories (for example: <\$20,000, \$20,000-34,999, \$35,000-49,999, \$50,000-\$99,999, ≥\$100,000, prefer not to answer) and recorded by self-report
- **Self-Rated Health Status:** Single-item assessments of self-rated health status have a strong association with health outcomes¹⁴²⁻¹⁴⁸ and provide a broad assessment of health.¹⁴⁹ Self-rated health will be measured using the following question/responses similar to: "In general, would you say your health is Excellent, Very Good, Good, Fair, or Poor?", which has been used in nationally representative samples.¹⁴⁷⁻¹⁴⁹
- **Health literacy** (i.e., the ability to obtain, process, and understand basic information to make appropriate health decisions)¹⁵⁰⁻¹⁵² will be evaluated using a Rapid Estimate of Adult Literacy in Medicine instrument.^{33,153,154}
- **Baseline comorbidities** (examples: dyslipidemia,¹⁵⁵ anxiety,¹⁵⁶ depression,¹⁵⁷ diabetes mellitus,¹⁵⁸ chronic kidney disease¹⁵⁹) will be assessed via self-report and the electronic health record using established ICD codes as per previous research.^{50,60,65,66,155-159}
- **Social Support** will be evaluated using a brief multi-dimensional evaluation validated for patients' chronic illnesses (example: The Medical Outcomes Study Social Support Survey).^{149,160-162}
- **Global medication adherence** will be assessed using the Morisky adherence scale.^{163,164}

Baseline Electronic Health Record and Other Database Data Collection

- **Healthcare utilization** will be evaluated using the John Hopkins Adjusted Clinical Group Case-Mix System, which assesses morbidity burden based on patient age, gender, and patterns of disease,^{50,60,66,165} the number of clinic visits will be measured.
- **Baseline antihypertensive medications and other medications:** Number of antihypertensive medication classes will account for varying hypertension treatment at baseline. Data will be acquired from the electronic health record and participant self-report, and will include prescription and non-prescription medications.
- **Primary care provider characteristics** (age, gender, specialty, time since completed medical school, % of panel with hypertension, panel size) will be obtained when available from the electronic health record and/or the American Medical Association Masterfile data.^{50,60}

Interviewer-Administered Data Collection (Baseline, 6 months, and 12 months)

- **Physical Activity.** We will assess physical activity using the Godin Exercise Questionnaire to evaluate weekly leisure activity and total leisure activity.
- **Automated Self-Administered 24-Hour (ASA24) Dietary Assessment Tool** – A web-based tool that enables multiple, automatically coded, self-administered 24-hour recalls. This tool will be used to assess, for example, sodium, fruit, and vegetable intake in relation to the DASH-sodium diet.

Blood Pressure Measurements

Blood pressures at each research site will be assessed with a Dinamap Monitor. Cuff size will be determined by arm circumference. An appropriate sized¹⁶⁶ blood pressure cuff will be connected to an automated sphygmomanometer (Dinamap). Each site will have the following cuff sizes available: small adult (for arm circumference of 22-26 cm), regular adult (27-34 cm), and large adult (35-42 cm). A blood pressure measurement will be obtained on the right upper arm, then the left upper arm, for the initial assessment. Right arm blood pressures will be subsequently used for the initial and follow-up visits, unless the left arm systolic blood pressure is ≥10 mmHg higher. The average of the second and third systolic and diastolic pressures, each taken 1 minute apart, will define the baseline clinic blood pressure.¹⁶⁷ If a participant's upper arm is too large, a forearm blood pressure will be obtained. All participants (intervention and control) will receive copies of their baseline, 6-month, and 12-month research clinic blood pressures to share with their usual healthcare provider, and will receive instructions on recommended primary care clinic follow-up.^{43,168}

24-Hour Blood Pressure Monitoring:¹⁶⁹⁻¹⁷¹ 24-hour blood pressure monitoring will take place at baseline, 6 months, and 12 months. Staff trained in the use of the 24-hour ambulatory blood pressure monitor will apply the appropriate sized cuff to the subjects' non-dominant arms unless the systolic blood pressure difference as measured during the clinic blood pressure assessment is >10 mmHg, in which case the arm with the highest value obtained

will be used. ABPM placement procedures and device recording setting will be per the AMBP manufacturing company's instructions and hypertension guideline recommendations. Participants will be instructed to keep their arm still during cuff inflation, and on the use of a diary to record the time of their activities, sleep, symptoms, and medications. Participants will be given instructions on how and when to return the device to study staff. Data from the returned device will be uploaded and time-matched with information from the participants' diaries. Day-time and night-time will preferentially be defined using each participant's diary. All acquired readings will be saved and used for analysis. If the participant is unable to complete ambulatory blood pressure monitoring, they will not be excluded, but will alternatively have their blood pressure evaluated for study eligibility using the automatic office blood pressure (AOBP) technique per the SPRINT protocol¹⁷² (example: have serial blood pressures acquired once every 5 minutes up to 5 times, using an automatic cuff without a research staff member present [i.e., while sitting alone in the research clinic exam room]).

Home Blood Pressure Monitoring: Intervention participants will be provided an Omron home blood pressure monitor with an appropriate cuff size; details of the final model acquired for the study can be found in the appendix.^{173,174} The selected monitor will be based upon validation studies in young adults and also across BMI categories.¹⁷⁵ Intervention arm participants will receive training and practice on proper cuff placement and monitor use during their baseline enrollment visit.³⁶ They will be asked to take their blood pressure at least three days a week, 2 measurements each time.^{31,36} A normal home blood pressure (complicated and uncomplicated hypertension) is <135/85 mmHg,¹⁷⁶ which accounts for changes in hypertension guidelines for patients with diabetes and chronic kidney disease.^{21,177} Participants will be able to read the recorded blood pressures to their health coach during the scheduled health coach phone calls (see below).¹⁷⁸ Participants will be asked to bring their home blood pressure monitor to the 6- and 12-month visits to review recorded blood pressures. Participants will keep the blood pressure monitor after study completion. Malfunctioned monitors will be replaced during the study.

